Our overall research goal is to evaluate the clinical utility of preoperative pessary placement as a part of patient counseling or preparation for surgery. In this protocol we aim to increase patient preparedness for surgery, patient satisfaction, and post-operative quality of life in adult women scheduled for surgery for symptomatic pelvic organ prolapse. To accomplish this, following counseling regarding all treatment options for prolapse, we will perform a prospective case-crossover study where 112 subjects who elected for surgical management will utilize a pessary for 1-4 weeks prior to undergoing prolapse surgery.

We propose:

Specific aim 1a: To evaluate concordance of the Patient Global Impression of Improvement Score between vaginal pessary use (assessed prior to surgery) and surgical intervention (assessed at 3 months postoperatively) for women with pelvic organ prolapse. *Hypothesis:* There is a strong correlation between the self-reported Patient Global Impression of Improvement Score following pessary use and surgery, as assessed at 3 months post-operatively.

Specific aim 1b.) To evaluate concordance in symptomatic change in pelvic and voiding symptoms (measured by validated symptom questionnaires) from baseline between pessary use (assessed prior to surgery) and surgical intervention (assessed at 3 months postoperatively). *Hypothesis:* There is a strong correlation between the changes in pelvic and voiding symptoms following pessary use and surgery, as assessed at 3 months post-operatively

Specific aim 2: To evaluate the impact of preoperative pessary use on patient preparedness for surgery (measured by validated questionnaire) as compared between the initial office consultation and following 1-4 weeks of pessary use.

Hypothesis: Preoperative pessary use will increase self-reported preoperative patient preparedness for surgery compared to office counseling alone.

II. Research Strategy

1. Significance:

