The proposed project is a new approach to addressing the gaps in patient counseling and preparedness for surgery that currently exist. The proposed protocol will clarify the utility of pessary placement given the noted heterogeneity in current clinical practices. Additionally, while pessaries are at times used clinically to help differentiate potential symptoms that may improve with surgery, this is an empirical rather than evidence-based practice. Thus, correlation of symptomatic change in bladder, bowel or pain symptoms with pessary use and surgery is important for pre-operative counseling. Additionally, with recent evidence regarding the importance of preoperative patient preparedness on surgical outcomes and patient satisfaction, evaluating the use of a pessary as part of patient education and preoperative preparation may highlight a potential innovative, low-cost, low-risk, and widely accessible tool for improving patient care and obtaining the best experience for our patients.

C. Approach- Experimental Design and Methods:

C.1. Study design and overview

Overview: This is a single center, prospective, case-cross over trial of pessary use prior to reconstructive pelvic floor surgery for pelvic organ prolapse. The goal of the study is to evaluate the comparative efficacy of pessary use on pelvic floor symptoms versus surgical correction. Additionally, we will assess the impact that preoperative pessary use has on patient self-reported preparedness for surgery.

Study procedure and design: All patients will undergo baseline symptom evaluation via validated questionnaire at the time of their initial office consultation. Following this, the patient will undergo pessary fitting at least 7 days prior to scheduled surgical prolapse repair. The pessary will be left in place and symptomatic change from baseline assessed via validated questionnaire roughly 4 weeks after use or immediately prior to surgery (i.e. with the pessary in place). The pessary will then be removed at the time of surgery, and the patient will undergo surgical correction of their pelvic organ prolapse (including all restorative surgical procedures, abdominal and transvaginal). A concomitant anti-incontinence procedure will be performed at the discretion of the treating physician in consultation with the patient. The patient's symptomatic

outcome from surgery will then be reassessed by validated questionnaire at 6 weeks and 3 months postoperatively. (See Study Design Flow Chart)

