C.2. Participants

Study population: The study will be open to women (over age 18) presenting for evaluation and management of symptomatic pelvic organ prolapse at Mayo Clinic (Rochester, MN), who elect to undergo surgical management.

Inclusion criteria: Female patients: 1) older than 18 years of age; 2) with symptomatic pelvic organ prolapse; 3) electing for surgical repair of pelvic organ prolapse (transvaginal or transabdominal) at least 7 days after office consultation. A minimum of one week was chosen as the duration of pessary use, as this was found sufficient in a study evaluating diagnosing occult urinary incontinence with pessary use prior to prolapse surgery;³⁶ 4) who understand and have signed written informed consent for preoperative pessary placement.

Exclusion criteria: Patients that: 1) have previously been managed with a pessary for pelvic organ prolapse; 2) patients undergoing obliterative prolapse surgery (i.e. Colpocleisis), 3) are scheduled for surgery for pelvic organ prolapse less than 7 days after office consultation 4) have an isolated rectocele; 5) have allergies to both latex and silicone; 6) have an active pelvic infection.

C.3. Outcome Assessment

The primary aim (1a) will be assessed using the 7-point Likert scale of the Patient Global Impression of Improvement (PGI-I).^{1, 35} Concordance will be estimated along with a 95% confidence interval. Patient's will be considered treatment success if they answer "much better" or "very much better" on the PGI-I scale.³⁵ The additional primary aim (1b) will be assessed using Lin's concordance correlation coefficient for responses to: Pelvic Organ Prolapse Distress Inventory-6 (POPDI-6) which measures prolapse symptom severity, Pelvic Floor Impact Questionnaire-7 (PFIQ-7) to evaluate patient bother from their bladder/vaginal/bowel symptoms, and the Overactive Bladder Symptom Score (OABSS). The secondary aim will be assessed by evaluating patient responses to a preoperative preparedness questionnaire. Patients will be considered prepared for surgery if they answer "strongly agree" on a 6-point Likert scale, with responses ranging from "strongly disagree" to "strongly agree" to the question: "Overall, I feel prepared for my upcoming surgery."²

C.4. Sample Size Considerations

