treatment (pessary and surgery): Pelvic Floor Impact Questionnaires (PFIQ-7),³⁷ Pelvic Organ Prolapse Distress Inventory 6 (POPDI-6),³⁷ and Overactive Bladder Symptom Score (OABSS).³⁸ Thus, questionnaire assessments will be completed at the time of initial consultation, immediately prior to surgery (after pessary use), at 6 weeks postoperatively during office consultation, and via mailed questionnaires and phone interviews at 3 months. Patient preparedness for surgery will be assessed via validated questions after completing the standard office based counseling and signing the surgical informed consent (prior to pessary use), as well as immediately prior to surgery (after pessary use), according to validated questions evaluating self-reported preparedness for pelvic surgery.² Furthermore, following treatment with a pessary (prior to surgery), at 6 weeks and 3 months after surgery patients will complete the Patient Global Impression of Improvement (PGI-I) question.^{1, 35} All adverse events associated with pessary use or surgery will be documented and abstracted.

Baseline characteristics for the patients included in the trial will be reported as median with inter-quartile range for continuous variables and counts with percentages for categorical variables. The percent concordant will be calculated along with the corresponding 95% confidence interval. Given the paired nature of the data (post-pessary vs. post-surgery), differences between the two time points for dichotomous responses will be assessed using McNemar’s test whereas differences between ordinal responses will be assessed using Bowker’s test for symmetry. The correlation between the two time points for summary scores from validated questionnaires (POPDI-6, PFIQ-7, OABSS) will be assessed using Lin’s concordance correlation coefficient. All calculated p-values will be two sided and will be considered significant if < 0.05.

Study Schedule	Initial visit	After pessary use, day of surgery	Surgery	6 wks after surgery (clinic visit)	3 mos after surgery (mailing)
Medical History and Physical	X				
Informed Consent	X				
Pessary Fitting	X				
Preparedness for Surgery	X	X			
PFIQ-7	X	X		X	X
POPDI-6	X	X		X	X
OABSS	X	X		X	X
PGII		X		X	X
Surgery			X		

C.6. Potential limitations of the study design and alternative strategies:

Potential Limitations:

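### Aim 1b asks whether changes from baseline agree, but the analysis text applies Lin's coefficient to post-treatment scores, and the two coefficients can differ widely

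*Combined protocol and SAP*

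**What the plan says.** Specific aim 1b (section I) is "To evaluate concordance in symptomatic change in pelvic and voiding symptoms (measured by validated symptom questionnaires) from baseline between pessary use" and surgical intervention, with the surgical assessment at 3 months. Its hypothesis is "There is a strong correlation between the changes in pelvic and voiding symptoms following pessary use and surgery, as assessed at 3 months". Section C.1 uses the same idea for the pessary assessment: "symptomatic change from baseline assessed via validated questionnaire roughly 4 weeks after use".

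Section C.3 ties a statistic to the aim: "The additional primary aim (1b) will be assessed using" Lin's "concordance correlation coefficient for responses to" POPDI-6, PFIQ-7 and OABSS. The analysis paragraph of C.5 is more specific: "The correlation between the two time points for summary scores from validated questionnaires (POPDI-6, PFIQ-7, OABSS) will be assessed" by the same coefficient. The sentence before it identifies the pair of time points: "Given the paired nature of the data (post-pessary vs. post-surgery".

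The three instruments are completed at the initial consultation, immediately before surgery, and then "at 6 weeks postoperatively during office consultation, and via mailed questionnaires and phone interviews at 3 months". Baseline scores therefore exist, but no analysis sentence uses them to form a change score.

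**The concern.** The aim and its hypothesis concern changes. The analysis text, on its natural reading, concerns score levels after each treatment. These are different questions. Scores after pessary and after surgery can agree well simply because some women report few symptoms at every visit and others report many, whatever either treatment did. They can also agree poorly while the two changes agree well, if both treatments compress the range of scores.

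If C.5 is followed as written, the coefficient reported for an additional primary aim neither supports nor refutes the hypothesis stated for it. If the matter is left open until the data are in, someone will have to choose between two coefficients after seeing both.

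**Working it through.** **No plan figure to reproduce.** The documents state no expected CCC, precision or sample size for Aim 1b. The 62 patients in C.4 come from PGI-I concordance (1.96² × 0.8 × 0.2 / 0.1² = 61.5, rounded up to 62), and the 84 and 112 come from Aim 2. None depends on this point.

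**Notation.** B, P and S are the baseline, post-pessary and post-surgery scores on one instrument. Lin's coefficient for a pair is

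CCC = 2·cov / (v1 + v2 + (m1 − m2)²).

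**What cancels.** (P − B) − (S − B) = P − S, so the mean difference and the expected squared difference are the same on both scales. The variances and covariance are not.

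**Closed form.** Assume var(P) = var(S) = 1, SD(B) = k, corr(P,B) = corr(S,B) = ρ, corr(P,S) = q and equal means. Put D = k² − 2ρk. Then

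- var(P − B) = var(S − B) = 1 + D
- cov(P − B, S − B) = q − 2ρk + k² = q + D
- score CCC = q
- change CCC = (q + D)/(1 + D)
- change CCC minus score CCC = D(1 − q)/(1 + D)

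Since D = k(k − 2ρ), the two coincide only when ρ = k/2. The score CCC is the higher if ρ > k/2 and the lower if ρ < k/2.

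**Illustrations (all inputs assumed).**

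| Case | D | Score CCC | Change CCC |
|---|---|---|---|
| k = 1, q = 0.5, ρ = 0.3 | 0.4 | 0.50 | 0.9/1.4 = 0.64 |
| k = 1, q = 0.5, ρ = 0.5 | 0 | 0.50 | 0.50 |
| k = 1, q = 0.5, ρ = 0.7 | −0.4 | 0.50 | 0.1/0.6 = 0.17 |
| Widening: changes independent of each other and of baseline, change variance half the baseline variance | – | 1/1.5 = 0.67 | 0 |
| Narrowing: k = 2, ρ = 0.5, q = 0.25 | 2 | 0.25 | 2.25/3 = 0.75 |

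In the widening case the post-treatment SD is √1.5 = 1.22 times the baseline SD. In the narrowing case it is half.

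**Unequal means.** If the post-treatment means differ by g = 0.5 post-treatment SD, add h = g²/2 = 0.125 to each denominator. For k = 1, q = 0.5, the score CCC is 0.5/1.125 = 0.44, and the change CCC is 0.59, 0.44 or 0.14 for ρ = 0.3, 0.5 or 0.7. The pattern is unchanged.

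**Against sampling error.** Simulating normal samples at the planned sizes gives an approximate 95% half-width for a score CCC of 0.50 of 0.19 at n = 62 and 0.16 at n = 84. Both coefficients come from the same women, so the better yardstick is the half-width of their difference:

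| Case | Gap | n = 62 | n = 84 |
|---|---|---|---|
| ρ = 0.3 | 0.14 | 0.15 | 0.13 |
| ρ = 0.7 | 0.33 | 0.22 | 0.19 |
| Widening | 0.67 | 0.20 | 0.17 |
| Narrowing | 0.50 | 0.20 | 0.17 |

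The smallest non-zero gap is about the size of the noise. The others clearly exceed it.

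**The case against.** The strongest reply is that this is loose wording rather than a substituted analysis. C.3 names the instruments, not the scale, and refers back to an aim already defined as change. That is fair for C.3. It does not rescue C.5, which names summary scores at two post-treatment time points. C.1 also helps the concern less than it might: it speaks of change from baseline for the pessary assessment only, and for surgery it speaks of reassessing the outcome.

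A second reply is that change scores are not obviously the better analysis, because the shared baseline couples them. This has force. In the narrowing case the partial correlation of the two post-treatment scores given baseline is (q − ρ²)/(1 − ρ²) = 0, so the pessary result adds nothing about surgery beyond baseline, yet the change CCC is 0.75. With q = 0, ρ = 0 and k = 1, the change CCC is still 1/2 = 0.50. A high change CCC therefore needs a caveat and a companion figure. That does not make the score CCC an answer to an aim worded in terms of change.

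Third, the plan sets no threshold for a strong correlation and no test for Aim 1b, so no formal decision would flip, and either coefficient can be computed later from the scheduled data. This is true, and it limits the consequence to what is reported and how it is interpreted.

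**Conclusion.** The mismatch stands, and nothing elsewhere in the documents resolves it. Followed as written, C.5 gives a coefficient for agreement of scores where the aim and its hypothesis call for agreement of changes. That conclusion rests on the text alone.

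The size is illustrative. It depends on standard deviations and correlations that the documents do not give, on equal post-treatment SDs and on equal correlations with baseline; the main figures also take equal means. In the examples with a score CCC of 0.50, the change CCC runs from 0.17 to 0.64. More extreme but coherent configurations give 0.67 against 0, and 0.25 against 0.75. The direction is unknown. The point should be fixed before analysis because Aim 1b is given primary standing; it does not threaten the design or the data.

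**What to change.** In C.3 and C.5, state that the Aim 1b coefficient is Lin's CCC between (post-pessary minus baseline) and (3-month postoperative minus baseline), computed separately for POPDI-6, PFIQ-7 and OABSS, each with a 95% confidence interval. Carry the 3-month visit across from the aim, since C.5 says only post-surgery and the instruments are also collected at 6 weeks. Label any 6-week version secondary.

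Add a sentence noting that the shared baseline can by itself raise or lower this coefficient. Report the CCC of post-pessary against 3-month scores alongside it as supportive, described as agreement of scores rather than of changes.

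The cost is wording and a little extra analysis. All three instruments are already scheduled at baseline, post-pessary, 6 weeks and 3 months, and the figures of 62, 84 and 112 are unaffected. The reported coefficient may turn out higher or lower than the score-based one.

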Management options for symptomatic prolapse include pelvic floor physical therapy, vaginal pessary and a variety of reconstructive surgical techniques. Following appropriate patient counseling regarding these options, patients choose a therapy based on the known efficacies and risks for each, as well as how they perceive that the treatment will help them accomplish their individual treatment goals. For instance, while a pessary may provide symptomatic relief, it can impact sexual function and needs to be periodically removed and cleaned, which some patients may not prefer. Conversely, while surgery offers a more permanent treatment that restores the pelvic anatomy, it also carries greater risks.

Notably, both pessary use and surgery have been associated with adequate symptomatic improvement, however in disparate patient populations, which makes direct comparisons of outcomes difficult. Additionally, while some symptoms, such as a sensation of a vaginal bulge, are consistently linked to the severity of prolapse, the associations of bowel, overactive bladder or abdominal/pelvic pain symptoms and the stage of anatomic prolapse are less well defined. Uncertainty of symptomatic improvement and unrealistic patient expectations about surgery can lead to decreased patient satisfaction and poor symptomatic outcomes.

In cases of equivocal symptoms, some providers utilize a vaginal pessary preoperatively to evaluate the potential role of a surgical correction. Conceptually, symptoms that improve with the use of a pessary may indicate surgically correctable symptoms, given the similar expected anatomic changes with pessary use and surgery. However, this is an empiric practice, rather than evidence-based. Additionally, the maximal degree of anatomic improvement between pessary use and surgery has not been well studied. Likewise, there are no prior studies evaluating the degree of symptomatic change with pessary use and surgery in the same patient.

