In pelvic organ prolapse treatment, presently, the pessary test is occasionally empirically used for cases of pelvic organ prolapse with equivocal symptomatology, in order to better inform preoperative counseling and shape patient expectations for prolapse surgery. Interestingly, while this is practiced empirically, there is no evidence available evaluating a correlation between symptom improvement with pessary use and surgical intervention. Thus, if improvement of overactive bladder symptoms, pain or bowel symptoms from pessary use mirrors that of surgery, universal preoperative pessary use may be a low-cost, low-risk, and widely accessible tool for addressing patient's unmet counseling needs.

A.4. Active participation of patients by utilizing a pessary prior to surgery could increase preparedness for surgery.

Despite standard office based preoperative counseling, a previous series from a large tertiary care center reported that only 58% of patients strongly agreed that they were prepared for the surgery. This is an important consideration as patient preparedness for pelvic organ prolapse surgery has been associated with patient satisfaction and subjective symptomatic outcomes, regardless of the anatomic outcome.²

Notably, numerous previous methods for improving patient education for surgery such as hand out leaflets,¹⁹ multimedia presentations,³¹ printing of personalized 3-D models,³² as well as decision aids³³ have been studied with mixed results. While these methods may potentially improve patient knowledge of the anticipated surgery, none allow for a demonstration of functional outcomes. As such, universal use of a pessary preoperatively, could uniquely improve patient preparedness for surgery by demonstrating the potential functional result of surgery.

B. Innovation

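### Aim 1b's single OABSS coefficient pools women with and without bladder symptoms at baseline; a restricted coefficient should be reported beside it

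*Combined protocol and SAP*

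**What the plan says.** Section C.3 makes this an additional primary aim: "The additional primary aim (1b) will be assessed using Lin's concordance correlation coefficient for responses to" POPDI-6, PFIQ-7 and OABSS. The analysis paragraph of C.5 repeats it: "The correlation between the two time points for summary scores from validated questionnaires (POPDI-6, PFIQ-7, OABSS) will be assessed using" Lin's coefficient. Neither section defines an analysis set for Aim 1b, a baseline-symptom restriction, a baseline adjustment or an analysis of PFIQ-7 by domain. That the coefficient covers all women with data is therefore inferred from the absence of any restriction.

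The Specific Aims state the hypothesis in terms of change: "There is a strong correlation between the changes in pelvic and voiding symptoms following pessary use and surgery". No number is attached to strong. C.5 refers to summary scores at two time points, so both changes and post-treatment scores are possible readings.

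The symptom criterion for entry in C.2 is women "with symptomatic pelvic organ prolapse"; no minimum OABSS or PFIQ-7 score is set. The Specific Aims also say that "the associations of bowel, overactive bladder or abdominal/pelvic pain symptoms and the stage of anatomic prolapse are less well defined". Section A.3 nevertheless names these symptoms as the reason for a pessary trial: universal use may help counseling "if improvement of overactive bladder symptoms, pain or bowel symptoms from pessary use mirrors that of surgery".

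**The concern.** A woman with no overactive bladder symptoms at baseline will usually score about zero on OABSS after the pessary and again after surgery, and her two changes will also be about zero. Put in one coefficient with symptomatic women, such women form a cluster near (0,0). Lin's coefficient reads the gap between that cluster and the symptomatic women as agreement between treatments. That gap shows who had the symptom, not whether a symptom that improves with the pessary will improve with surgery.

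The question in A.3 is about improvement, which only women with the symptom can show. A moderate OABSS coefficient could be taken as support for using a pessary trial to predict bladder outcomes when it reflects only the mix of women enrolled. No other planned analysis would reveal this. McNemar's and Bowker's tests compare marginal distributions, and the hypothesis has no threshold.

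**Working it through.** **Plan's own figures.** C.4 gives none for Aim 1b. Its figures for the other aims reproduce or nearly so: 1.96² × 0.80 × 0.20 / 0.10² = 61.5, hence 62 for PGI-I (50/62 gives 70.8–90.5%). The 84 completers for Aim 2 compare with 83 from one standard paired-proportions formula (others give 88 and 91), and 84 / 0.75 = 112. They do not bear on this point, except that 84 is used below as the number of completers.

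**Inputs.** The documents give no share of symptom-free women and no score means or SDs. Assumed: a share q = 0.3 to 0.5 at (0,0); symptomatic women with the same SD s after both treatments, means m_P (pessary) and m_S (surgery), and no association between the two. Write k = m/s.

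**Formula.** Lin's coefficient is 2·cov / [var_P + var_S + (difference in means)²]. For the mixture:
- cov = q(1−q)·m_P·m_S
- var = (1−q)s² + q(1−q)m², for each treatment
- difference in means = (1−q)(m_P − m_S)

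Dividing through by (1−q)s² and collecting terms:

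pooled coefficient = 2q·k_P·k_S / [2 + (k_P − k_S)² + 2q·k_P·k_S]

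With equal means this is qk² / (1 + qk²).

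| k_P, k_S | q = 0.3 | q = 0.5 |
|---|---|---|
| 0.5, 0.5 | 0.075/1.075 = 0.07 | 0.125/1.125 = 0.11 |
| 1, 1 | 0.3/1.3 = 0.23 | 0.5/1.5 = 0.33 |
| 2, 2 | 1.2/2.2 = 0.55 | 2/3 = 0.67 |
| 0.5, 1.5 | 0.45/3.45 = 0.13 | 0.75/3.75 = 0.20 |
| 1, 2 | 1.2/4.2 = 0.29 | 2/5 = 0.40 |

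The coefficient among symptomatic women is zero in every cell. If it were 0.3, with equal means, the pooled value would be (0.3 + qk²)/(1 + qk²): at k = 1, 0.6/1.3 = 0.46 and 0.8/1.5 = 0.53.

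**Noise and sample size.** Symptom-free women need not sit exactly at zero. In simulation, with independent changes of mean 4, SD 2.5 in symptomatic women and noise of SD 0.8 in the others, the pooled coefficient was 0.33, 0.49 and 0.57 for 20%, 40% and 60% symptom-free. With 84 completers and 40% symptom-free, the central 95% range of the estimate was 0.30 to 0.64 pooled, and −0.28 to 0.27 in the roughly 50 symptomatic women. An approximate lower 95% bound exceeded zero in 99.7% of simulated trials pooled and in 2% restricted.

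**Restriction alone is not enough for changes.** Both changes subtract the same baseline. With baseline SD 3 and independent post-treatment scores of SD 2, two changes in symptomatic women have coefficient 9/(9 + 4) = 0.69; a simulation truncating scores at zero gave 0.72. Where each treatment independently removes a proportion of the baseline score, changes and post-treatment scores both gave 0.30 among symptomatic women, while the correlation of the proportional responses was 0.00. Post-treatment scores are thus not always free of the baseline either.

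**PFIQ-7.** Assume vaginal bother in all women, bladder and bowel bother each absent in a share q, and independent changes of mean 25, SD 17 per domain. Then cov = 2q(1−q)·25² and var = 17²·[1 + 2(1−q)] + cov:
- q = 0.3: 262.5/(693.6 + 262.5) = 0.27
- q = 0.5: 312.5/(578 + 312.5) = 0.35

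Requiring a baseline total above zero keeps every woman in this model, so 0.27 and 0.35 remain.

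**The case against.** The strongest case against has four parts.

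- **Women without the symptom are informative.** C.2 cites a study of pessary use to diagnose occult urinary incontinence, so the documents recognise that symptoms can appear with a pessary. A.3 contemplates universal use, and Aim 1b is not limited to women with bladder symptoms. This stands. A reader might infer that the all-women coefficient is wrong and should be replaced; the documents do not support that, because agreement across all candidates for surgery is a legitimate target.
- **PFIQ-7 does not behave like OABSS.** C.3 describes it as "Pelvic Floor Impact Questionnaire-7 (PFIQ-7) to evaluate patient bother from their bladder/vaginal/bowel symptoms", and every woman entered has symptomatic prolapse, so a cluster at zero on the total is not expected. This stands. What remains there comes from summing over domains that some women lack.
- **The size depends on chosen inputs.** This also stands: it is small at a mean of 0.5 SD, and Lin's coefficient penalises unequal means. For post-treatment scores, a mean of 1–2 SD requires substantial residual symptoms after both treatments.
- **The hypothesis is of strong correlation, and much of the range is only moderate.** This carries less weight, since no threshold separates the two.

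None of these removes the exposure of OABSS, where absence of the symptom at baseline is compatible with entry.

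**Conclusion.** The point holds as a cheap improvement, mainly for OABSS. The single all-women coefficient can be raised by women without overactive bladder symptoms when pessary response predicts nothing among those who have them. With 30–50% symptom-free and no association in symptomatic women, the pooled value is 0.07–0.11 at mean/SD 0.5, 0.23–0.67 at mean/SD 1–2 with equal means, and 0.13–0.40 when the two means differ by 1 SD. All of these inputs are assumptions.

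A reader might go further and conclude that the plan will report false concordance. The documents do not support that: they give neither the share of symptom-free women nor the score distributions, and zero association is the extreme case. POPDI-6 measures prolapse symptoms and is largely unaffected.

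**What to change.** In C.3 and C.5:

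- **OABSS.** Keep the all-women coefficient. Beside it, prespecify one restricted to women with the symptom at baseline, with the cut fixed before the data are opened. Base any statement that pessary improvement of bladder symptoms mirrors surgery on the restricted one.
- **Shared baseline.** Give the restricted result for changes and also for post-treatment scores or adjusted for baseline. Adjustment is the safer of the two if responses are proportional to baseline.
- **PFIQ-7.** Report by bladder, bowel and vaginal domain, each among women with that domain affected at baseline.
- **Women without the symptom.** Count new symptoms after pessary and after surgery.

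Baseline OABSS and PFIQ-7 are already in the study schedule, so the cost is SAP wording and a few extra runs. The price is precision: with 84 completers and 30–50% symptom-free, about 59 to 42 women remain for OABSS (84 × 0.7 and 84 × 0.5). Intervals will be wider and the coefficient probably lower.
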